The above criteria should also be used for AEs for the phase 2 part of the trial. Safety will be assessed by AEs, SAEs, vital signs, physical examinations, and review of biochemistry and hematology laboratory values.

After completion of the first cycle / DLT-assessment period, further toxicities will be managed as for patients treated on the phase 2 portion of the study. Patients who do not achieve a CR or PR after the first cycle of therapy may continue therapy, with the duration of therapy determined as outlined in section 6.5.

During the phase 2, guidance on how to manage common non-hematologic toxicities is given below. If a patient tolerates pinometostat at the MTD and azacitidine at 75 mg/m² but has a hematologic toxicity, the next cycle of azacitidine administration may be delayed out to day 42 while the pinometostat is continued. If the most recent bone marrow on treatment shows persistent leukemia, the patient may continue to be treated with combination therapy with supportive care given for cytopenias.

After discussion with the medical monitor, a lower dose of pinometostat therapy may be considered after the DLT period in the event of toxicities. The dose of azacitidine should remain constant at 75mg/m² daily for 7 days given over a 10-day period at the start of each cycle.

If recurrent hematologic toxicity occurs in someone who has achieved a remission, alternative dosing schedules of pinometostat could be explored as follows:

If the recommended phase II dose is 90 mg/m²/day

Dose Level	Pinometostat Dose
-1	54 mg/m ² /day CIV infusion
0	90 mg/m ² /day CIV infusion

If the recommended phase II dose is 54 mg/m²/day

Dose Level	Pinometostat Dose
-1	36 mg/m ² /day CIV infusion
0	54 mg/m ² /day CIV infusion

Azacitidine administration may be held until up to day 42 of the cycle, but the dosage should not be reduced.

Indications for dose modifications of pinometostat are as follows. For specific concerns not outlined here, please contact the medical monitor.

Nausea	Management/Next Dose for Pinometostat
≤ Grade 1	Continue administration, provide supportive care, monitor
Grade 2	Continue administration, provide supportive care, monitor

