Grade 3	Provide supportive care. If tube feeding or TPN are required due to nausea and there is no improvement to ≤ Grade 2 after three days of supportive treatment as per local institutional practice, hold pinometostat until nausea has resolved to ≤ Grade 2. Pinometostat should restarted at one dose level lower.
Grade 4	N/A
*Patients requiring a delay of >2 weeks should go off protocol therapy.	
**Patients requiring > one dose reductions should go off protocol therapy.	
Recommended management: antiemetics.	

Vomiting	Management/Next Dose for Pinometostat
≤ Grade 1	Continue administration, provide supportive care, monitor
Grade 2	Continue administration, provide supportive care, monitor
Grade 3	Provide supportive care. If tube feeding or TPN are required due to vomiting and there is no improvement to ≤ Grade 2 after three days of supportive treatment as per local institutional practice, hold pinometostat until vomiting has resolved to ≤ Grade 2. Pinometostat should restarted at one dose level lower.
Grade 4	Hold therapy until vomiting has resolved to ≤ Grade 2, restart at lower dose if appropriate**
*Patients requiring a delay of >2 weeks should go off protocol therapy.	
**Patients requiring > 1 dose reductions should go off protocol therapy.	
Recommended management: antiemetics.	

Diarrhea	Management/Next Dose for Pinometostat
≤ Grade 1	Continue administration, provide supportive care, monitor
Grade 2	Continue administration, provide supportive care, monitor
Grade 3	If ongoing x 48h, hold therapy until ≤ Grade 2, restart at same dose.

Diarrhea	Management/Next Dose for Pinometostat
	Pinometostat should restarted at one dose level lower*.
Grade 4	Hold therapy until \leq Grade 2, restart at lower dose if appropriate**

Recommended management: Loperamide antidiarrheal therapy Dosage schedule: Adults- 4 mg at first onset, followed by 2 mg with each loose motion until diarrhea-free for 12 hours (maximum dosage: 16 mg/24 hours) Children – 2mg TID dosing may be used for children who are small for their chronological age but are 30kg or greater Adjunct anti-diarrheal therapy is permitted and should be recorded when used. *Patients requiring a delay of >2 weeks should go off protocol therapy. **Patients requiring > one dose reduction should go off protocol therapy.
	

Fever	Management/Next Dose for Pinometostat
\leq Grade 1	Continue administration, monitor
Grade 2	Continue administration, monitor

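### The Grade 3 diarrhea row gives two contradictory restart doses for pinometostat, and Section 7 does not say when each applies

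*Combined protocol and SAP*

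**What the plan says.** Section 7 manages pinometostat toxicity with one table per toxicity. In the diarrhea table the only action column is headed for pinometostat. The Grade 3 entry reads "If ongoing x 48h, hold therapy until ≤ Grade 2, restart at same dose" and carries on, after a page break and before the Grade 4 row, with "Pinometostat should restarted at one dose level lower".

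That second sentence carries a single asterisk, which leads to "Patients requiring a delay of >2 weeks should go off protocol therapy". Grade 4 diarrhea has its own row: hold, then "restart at lower dose if appropriate", with a double asterisk leading to "Patients requiring > one dose reduction should go off protocol therapy".

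The text before the tables adds two general statements. After cycle 1 of phase 1b, "further toxicities will be managed as for patients treated on the phase 2 portion of the study", so the tables cover those patients as well as phase 2 patients. It also says: "After discussion with the medical monitor, a lower dose of pinometostat therapy may be considered after the DLT period in the event of toxicities".

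**The concern.** The two sentences give opposite instructions for the same drug, grade and event. Two sites reading the same row could restart similar patients one dose level apart.

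Two things are at stake. The first is dose, and with it safety and consistent treatment after a toxicity that can be expected: Section 10.1 lists diarrhea as possibly related to pinometostat and among the likely events (over 20%) for azacitidine. The second is staying on treatment. Only one dose reduction is allowed, so the choice of sentence decides whether that allowance is spent, and in some patients whether protocol therapy ends.

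**Working it through.** No figure in the plan needs reproducing. The check asks whether any text separates the two instructions, and then sizes the difference.

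**1. Does any text reconcile them?**

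- *Different drugs?* No. The column is for pinometostat. Azacitidine has its own labelled column where it is meant (the bone marrow hypocellularity table), and Section 7 says its dose is not to be reduced. The Grade 4 diarrhea row uses the same hold-and-restart phrasing with a lower dose, which can therefore only mean pinometostat.
- *Different grades?* No. The second sentence falls before the Grade 4 row, which has its own instruction.
- *The footnote?* No. The single asterisk is a rule for stopping therapy after a long delay. It does not choose a dose.
- *The general text?* No. The sentence on a lower dose after discussion with the medical monitor is permissive and gives no criterion. The advice to contact the monitor is for concerns the tables do not cover, and Grade 3 diarrhea is covered.
- *First versus recurrent episode?* A plausible intention, but written nowhere.
- *Sections 7.1 to 7.3?* Section 7.1 mentions diarrhea only as a reason to check the EKG and electrolytes. Sections 7.2 and 7.3 do not address it.

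**2. What do the other rows do?** These are the entries in Section 7 that hold pinometostat and state a restart dose:

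| Entry | Condition for the hold | Restart dose |
|---|---|---|
| Nausea, Grade 3 | Tube feeding or TPN, and three days without improvement | One level lower |
| Vomiting, Grade 3 | Same as nausea | One level lower |
| Vomiting, Grade 4 | None beyond grade | Lower, if appropriate |
| Fever, Grades 3 and 4 | None beyond grade | One level lower |
| Anemia, neutropenia, thrombocytopenia, Grade 4 | Drug-related, at least 14 days | Dose level -1 |
| QTcF, Grade 3 (Section 7.1) | None beyond grade | Reduced |
| Diarrhea, Grade 4 | None beyond grade | Lower, if appropriate |
| **Diarrhea, Grade 3** | **Ongoing for 48 hours** | **Same, and one level lower** |

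The nausea and vomiting rows are imperfect comparators because their trigger is stricter ("If tube feeding or TPN are required due to nausea and there is no improvement" for nausea). Fever has no such condition and still lowers the dose. The disputed sentence also repeats the wording of the nausea, vomiting and fever rows, down to the same missing word. Restarting at the same dose appears only in the diarrhea cell.

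**3. Size of the dose difference.** The dose levels in Section 6.1 are 36, 54 and 90 mg/m²/day.

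- Assigned 90: 90 − 54 = 36 mg/m²/day; 36 / 90 = 40.0% lower.
- Assigned 54: 54 − 36 = 18 mg/m²/day; 18 / 54 = 33.3% lower.

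**4. Effect on the one permitted reduction.**

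| Patient | Same-dose reading | Lower-dose reading |
|---|---|---|
| Already reduced once, then Grade 3 diarrhea for 48 hours | Restarts at current dose | Needs a second reduction; off protocol therapy |
| Grade 3 diarrhea first, later toxicity needing a reduction | Later event takes the one reduction; stays on | Later event needs a second reduction; off protocol therapy |
| Grade 3 diarrhea only | No reduction used | One reduction used; stays on |

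No patient count can be computed, because the documents give no rate of Grade 3 diarrhea for the combination.

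**The case against.** The strongest reply is that the conflict is smaller than it looks. The trigger and the hold are unambiguous, so it would be wrong to infer that the whole row cannot be followed. Nearly all the surrounding evidence points to the lower dose. Section 7 brings the medical monitor into dose reductions, and Section 13.1 provides roughly weekly safety conferences plus investigator calls at least monthly in phase 1 and quarterly in phase 2, so silent divergence between sites is less likely. The row is also split by a page break, and strike-through would not survive extraction from PDF.

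Most of this stands as a limit on the point, but it does not remove it. The oversight meetings make a discrepancy easier to notice; they do not tell a site which dose to give. Nothing in the documents suggests that either sentence was struck out.

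A reader might also infer that the same-dose clause is certainly leftover text. The pattern of the other rows makes that likely, but a first-episode rule is also possible, and the documents do not settle it.

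A reader might further conclude that Grade 4 diarrhea needs tightening, because its wording is softer than a mandatory Grade 3 reduction. That does not follow. The qualifier there can equally govern whether to restart at all, so removing it could read as requiring a restart after a Grade 4 event. Grade 4 vomiting has the same wording, so the edit would also create a mismatch.

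**Conclusion.** The contradiction is real and confined to one element of one cell: the pinometostat restart dose after Grade 3 diarrhea lasting 48 hours. It applies in phase 2, and in phase 1b after cycle 1. The readings differ by 36 mg/m²/day (40%) at 90 mg/m²/day or by 18 mg/m²/day (33%) at 54 mg/m²/day, and they decide whether the single permitted reduction is used. The lower dose is the better supported reading, without proof of intent. The sponsor should correct it.

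This rests on two assumptions: that both sentences are current text, and that the limit of one reduction counts reductions for any toxicity, as its general wording suggests. The number of patients affected is unknown.

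Two wider inferences are not supported. The Simon design in Section 9.1 is unaffected: its stage sizes, response cut-offs and error rates do not depend on this row, and Section 9.5.2 keeps patients with incorrect dosing in the response analysis. The absence of a level below 36 mg/m²/day is a separate gap. It touches every row that lowers the dose by one level and would remain if this cell were corrected.

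**What to change.** Keep one instruction. The choice that is both better supported and more cautious is to delete the same-dose clause and attach each footnote to the step it governs:

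`Ongoing for 48 h: hold pinometostat until Grade 2 or lower*; resume one dose level lower**`

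If the sponsor intended the same dose for a first episode, write instead:

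`First episode: resume same dose. Recurrence: resume one dose level lower**`

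Leave the Grade 4 row unchanged, and do not add a rule for 36 mg/m²/day here.

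The cost is one table cell. Section 13.1 already requires an approved amendment before phase 2 enrollment, which is the latest sensible point. Phase 1b patients past cycle 1 already fall under the table, so the correction should reach sites sooner. The downside of the lower-dose rule is that some patients receive 33% to 40% less pinometostat after the event and use their one permitted reduction earlier.

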7.1 Guidelines for Management of QT Prolongation

The discussion of the emergency management of torsade de pointes and its hemodynamic consequences is beyond the scope of this guideline.

Both nonclinical and clinical data provided suggest a risk of QT prolongation with pinometostat, and the risk may be additive in combination with azacitidine. As such, a baseline EKG should be performed to evaluate for QT prolongation. A weekly EKG should be performed during cycle 1 to monitor for QT prolongation.

Subjects may be at increased risk for the development of QT prolongation when treated with pinometostat and azacitidine in combination with fluoroquinolones, azole antifungal agents or serotonin (5-HT₃) antagonists. Investigators need to be vigilant; refrain from administering concomitant medications associated with QT prolongation and if no other therapeutic options are available, monitor subjects receiving pinometostat and azacitidine with the combination of these drugs, and evaluate EKG and electrolytes (including potassium, magnesium, and calcium) particularly in subjects presenting with nausea, vomiting or diarrhea.

Subjects who experience prolongation of the QTc interval using Fridericia's equation (QTcF) interval to > 480 msec (CTCAE Grade ≥ 2) while treated with pinometostat and azacitidine should be promptly evaluated for causality of the QTcF prolongation and managed according to the following guidelines:

- Levels of electrolytes (potassium, calcium and magnesium) should be checked and supplementation given to correct any values outside the normal range.
- Concomitant therapies should be reviewed and adjusted as appropriate for medication with known QT prolonging effects.
- If no other cause is identified and the Investigator believes it is appropriate, particularly if QTcF remains elevated (after above measures have been implemented, or as determined by the Investigator), study drug may be interrupted, and an EKG should be rechecked in approximately 1 week after the QTcF prolongation was first observed or more frequently as clinically indicated. If QTcF has recovered or improved and the Investigator believes it is safe to do so, re-challenge with pinometostat should be considered if held.
- EKGs should be conducted at least weekly (e.g., at every scheduled visit) for 2 weeks following QTcF reduction ≤ 480 msec.

Grade 2 (QTcF > 480 and ≤ 500 msec)

- The dose of pinometostat may be reduced to a dose approved by the Medical Monitor without interruption of dosing. The pinometostat dose may be re-escalated to the prior dose in ≥ 14 days after QT prolongation has decreased to \leq Grade 1.

Grade 3 (QTcF > 500 msec)

- Hospitalization for continuous cardiac monitoring and evaluation by a cardiologist should both be considered.
- Dosing with pinometostat will be interrupted. If QTcF returns to within 30 msec of baseline or < 450 msec within 14 days, treatment may be resumed at a reduced dose
- The pinometostat dose cannot be re-escalated following dose reduction for Grade 3 QTcF prolongation unless the prolongation was associated with an electrolyte abnormality or concomitant medication

Grade 4 (QTcF > 500 msec or > 60 msec change from baseline with torsade de pointes or polymorphic ventricular tachycardia or signs/symptoms of serious arrhythmia)

- Subjects should be admitted to hospital for continuous cardiac monitoring and discharged only after review by a cardiologist.
- Dosing with pinometostat and azacitidine should be permanently discontinued.

7.2 Tumor Lysis Syndrome

Patients should be monitored for tumor lysis syndrome (TLS), which may be most likely to occur at the time of therapy initiation in patients with high tumor burden. TLS should be defined by the Howard criteria, with laboratory TLS defined by uric acid > 8.0mg/dL, phosphorus > 4.5 mg/dL, potassium > 6.0 mmol/L, and corrected calcium < 7.0 mg/dL with the presence of at least two abnormalities present during the same 24-hour period within 3 days prior to the start of therapy or 7 days afterward. Clinical tumor lysis syndrome is defined by cardiac dysrhythmia, sudden death, seizure, neuromuscular irritability, hypotension, heart failure, increasing creatinine of 0.3 mg/dL or a single value of 1.5 times the ULN, or oliguria (< 0.5 ml/kg/hr over 6 hours on average). See reference for further details.

Patients may receive prophylaxis and treatment for tumor lysis syndrome, including hydration, allopurinol, or rasburicase, as is appropriate per local institutional guidelines.

7.3 Differentiation Syndrome

Symptoms of differentiation syndrome may include fever, weight gain or edema, respiratory symptoms with or without infiltrates, pleural or pericardial effusions, hypotension, and acute renal failure. If differentiation syndrome is clinically suspected, initiate prompt administration of corticosteroids at a suggested dose of 10 mg dexamethasone IV or PO every 12 hours until resolution of symptoms and signs as well as hemodynamic monitoring, for a minimum of 3 days is recommended, until improvement. Hydroxyurea at a suggested dose of 1–4 g PO twice or three times per day may be used for subjects with leukocytosis in the setting of differentiation syndrome. Additionally, initiation of furosemide and/or prompt initiation of leukapheresis is recommended if clinically required. For all cases of suspected differentiation syndrome, pinometostat should be immediately held.

8. PHARMACEUTICAL INFORMATION

A list of the adverse events and potential risks associated with the investigational or commercial agents administered in this study can be found in Section 10.1.

8.1 CTEP IND Agent(s)

8.1.1 CTEP IND Agent #1 - Pinometostat (NSC #795144)

Chemical Name or Amino Acid Sequence: (2R,3R,4S,5R)-2-(6-amino-9H-purin-9-yl)-5-((((1r,3S)-3-(2-(5-(tert-butyl)-1H-benzo[d]imidazol-2-yl)ethyl)cyclobutyl)(isopropyl amino)methyl)tetrahydrofuran-3,4-diol

Other Names: EPZ-5676, EPZ005676

Classification: DOT1L inhibitor

CAS Registry Number: 1380288-87-8

Molecular Formula: C₃₀H₄₂N₈O₃

M.W.: 562.71 g/mol

Mode of Action: Pinometostat is a selective human DOT1-like, histone H3 methyltransferase (DOT1L) inhibitor. Pinometostat exhibits concentration and time depending inhibition of global methylation of lysine 79 of histone H3 (H3K79) in cultured cells. Pinometostat induces apoptosis in cells that accumulate in the G1/G0 phase. It also inhibits the expression of the key MLL fusion target genes HOXA9 and MEIS1.

Description: A clear to yellow liquid adjusted to a pH of 5.2-6.2 with 1N sodium hydroxide or 1N hydrochloric acid as needed.

How Supplied: Pinometostat is supplied by Epizyme, Inc. and distributed by the Pharmaceutical Management Branch, CTEP/DCTD/NCI. Pinometostat injection is provided as 100 mg/10 mL (10 mg/ml) solution in type 1 borosilicate glass serum vials closed with butyl rubber stoppers and aluminum overseals. The other components of the vial include hydroxypropyl betadex, citric acid, anhydrous, sodium hydroxide, hydrochloric acid, and water for injection.

Preparation: Pinometostat must be diluted with 0.9% sodium chloride injection, USP prior to administration to a final concentration between 0.54 mg/ml and 5.63 mg/ml. Add the calculated dose of pinometostat to the appropriate volume of 0.9% sodium chloride in a non-DEHP PVC, polyolefin, or EVA IV infusion bag. **Note: mixing of different drug lots in the same infusion bag should be avoided.** Then gently agitate the infusion bag to ensure mixing. Up to a 90-hour dose may be prepared. An overfill volume of 10% or per institution policy can be prepared to allow for priming of the infusion set tubing. Sites should prepare the appropriate final infusion volume according to standard practice based on a constant flow rate.

Storage: Store at room temperature between 15 °C -30 °C.

If a storage temperature excursion is identified, promptly return pinometostat to 15 °C -30 °C and quarantine the supplies. Provide a detailed report of the excursion (including documentation of temperature monitoring and duration of the excursion) to [contact] for determination of suitability.

Stability: Stability studies are ongoing. The intravenous infusion is stable at room temperature and can be infused for a maximum of 90 hours. The infusion bag can be stored at room temperature prior to infusion; the total time in bag, including both preparation and infusion time, should not exceed 114 hours total. The infusion must be completed within 114 hours after infusion bag preparation.

Route and Method of Administration: Continuous, intravenous infusion via central venous catheter with a pump for up to 90 hours at a constant flow rate. Compatible IV infusion sets are non-DEHP PVC, polyolefin, or EVA with or without a 0.2-micron filter.

Potential Drug Interactions: Pinometostat is metabolized in vitro predominantly by CYP3A with a minor contribution from CYP2C19. It is also a substrate for MATE2-K and likely a weak substrate for OATP1B3, MATE1, and P-gp. Pinometostat is not a substrate for OCT1, OCT2, OATP1B1 or BCRP. Use of strong CYP3A inhibitors and inducers should be avoided. Use caution when administered with strong inhibitors and inducers of CYP2C19, OATP1B3, P-gp, MATE1, and MATE2-K.

Pinometostat is a weak to moderate inhibitor of CYP3A4/5 in vitro. Pinometostat is an inhibitor of MATE1 and MATE2-K in vitro but not CYP1A2, 2B6, 2C8, 2C9, 2C19, 2D6, P-gp, BCRP, OAT1, OAT3, OCT1, OCT2, OATP1B1, OATP1B3 or BSEP. Use caution with concomitant use of other CYP3A and MATE1 and MATE2-K substrates, especially those with a narrow therapeutic window.

Pinometostat is not an inducer of CYP1A2, 2B6, or 3A4/5 activity or mRNA levels.

Patient Care Implications: Women of child-bearing potential (WOCP) must use acceptable contraceptives while on pinometostat and for 4 weeks after the last dose of pinometostat. Males with partners that are WOCP must use acceptable methods of contraception while on pinometostat and for 90 days after the last dose of pinometostat. It is unknown if pinometostat is excreted in breast milk so should not be administered to nursing mothers.

Availability

Pinometostat is an investigational agent supplied to investigators by the Division of Cancer Treatment and Diagnosis (DCTD), NCI.

Pinometostat is provided to the NCI under a Collaborative Agreement between the

Pharmaceutical Collaborator and the DCTD, NCI (see Section 13.4).

8.1.2 Agent Ordering and Agent Accountability

8.1.2.1 NCI-supplied agents may be requested by eligible participating Investigators (or their authorized designee) at each participating institution. The CTEP-assigned protocol number must be used for ordering all CTEP-supplied investigational agents. The eligible participating investigators at each participating institution must be registered with CTEP, DCTD through an annual submission of FDA Form 1572 (Statement of Investigator), NCI Biosketch, Agent Shipment Form, and Financial Disclosure Form (FDF). If there are several participating investigators at one institution, CTEP-supplied investigational agents for the study should be ordered under the name of one lead participating investigator at that institution.

In general, sites may order initial agent supplies when a subject is being screened for enrollment onto the study.

Submit agent requests through the PMB Online Agent Order Processing (OAOP) application. Access to OAOP requires the establishment of a CTEP Identity and Access Management (IAM) account and the maintenance of an “active” account status, a “current” password, and active person registration status. For questions about drug orders, transfers, returns, or accountability, call or email PMB any time. Refer to the PMB’s website for specific policies and guidelines related to agent management.

8.1.2.2 Agent Inventory Records – The investigator, or a responsible party designated by the investigator, must maintain a careful record of the receipt, dispensing and final disposition of all agents received from the PMB using the appropriate NCI Investigational Agent (Drug) Accountability Record (DARF) available on the CTEP forms page. Store and maintain separate NCI Investigational Agent Accountability Records for each agent, strength, formulation and ordering investigator on this protocol.

